1. VAS, ROM
2. Implant Status/Disposition
3. Document concomitant medications and/or therapies associated with an AE, SA(D)E
4. Review the subject's chart for AEs, SAEs and Device Deficiencies including inter-operative. AEs, SAEs and DevDs should be documented from the time of surgery through the study duration.
5. Complete the End of Study CRF.

13.3 CONCOMITANT MEDICATIONS AND THERAPIES

Any concomitant medications associated with an AE, SAE or SADE will be recorded. Concomitant medications will be recorded from the time of surgery through 12 months. If the subject's final visit occurred at 6 months, concomitant medications will be collected through 6 months.

14. STATISTICAL DESIGN

A Statistical Analysis Plan (SAP) will be written and finalized prior to database lock. The analyses specified in the protocol will be a microcosm of the detailed analyses to be contained in the SAP. If there are changes to or additional analyses required to the analysis described below, it will be described in the SAP and the Clinical Study Report (CSR).

14.1 GENERAL

Smith & Nephew's Global Biostatistics group or designee will conduct the statistical analysis for this study. Unless otherwise stated, all significance tests will be two-sided, performed at the 5%

CONFIDENTIAL AND PROPRIETARY

This document contains information that is confidential and proprietary to Smith & Nephew PLC and Smith & Nephew, Inc. and is intended for use only by Smith & Nephew and its manufacturer. It shall not be reproduced or copied in whole or in part, nor shall the contents be disclosed by any means without prior written permission from Smith & Nephew, nor shall anyone make any use of it that is contrary to the expressed or implied wishes of Smith & Nephew.

Study Protocol—Device	
PMCF Study on PEEK Suture Anchors for Hip Indications	Number: 2018.14.SMD.PEEK.RET.HIP
	Version: 2.0, 03 April 2019
	Page: 40 of 63

significance level. Resulting p-values will be provided and 95% two-sided confidence intervals will be generated where appropriate.

Where data summaries are specified, categorical and ordinal variables will be summarized with frequencies and percentages. Continuous variables will be summarized with the following summary statistics: number of observations, mean, median, standard deviation, minimum and maximum values. All analyses will be performed in SAS version 9.3 (or later).

14.2 ANALYSIS POPULATIONS

The following analysis populations will be used for this study:

- **Safety Population (SAF):** This includes all subjects who enroll in the study who had previously undergone hip repair using PEEK suture anchors, i.e. subjects who would provide retrospective data.
- **Per-Protocol Population (PP):** This includes all subjects in the Safety Population, who have no significant protocol deviations and who meet all the inclusion/exclusion criteria.

14.3 EFFICACY ANALYSIS

14.3.1 Analysis of Primary Endpoint

The rate (%) of clinical success of all the PEEK suture anchor devices combined at 6 months post-operative will be summarized as a frequency and percentage. A 95% two-sided exact CI for a single proportion will be presented using Clopper-Pearson's method [1]. The same type analysis would be carried out for each of the 2 different PEEK suture anchors used in the study. These

CONFIDENTIAL AND PROPRIETARY

This document contains information that is confidential and proprietary to Smith & Nephew PLC and Smith & Nephew, Inc. and is intended for use only by Smith & Nephew and its manufacturer. It shall not be reproduced or copied in whole or in part, nor shall the contents be disclosed by any means without prior written permission from Smith & Nephew, nor shall anyone make any use of it that is contrary to the expressed or implied wishes of Smith & Nephew.

Study Protocol—Device	
PMCF Study on PEEK Suture Anchors for Hip Indications	Number: 2018.14.SMD.PEEK.RET.HIP
	Version: 2.0, 03 April 2019
	Page: 41 of 63

analyses will be carried out using the per protocol population as the primary analysis population with the safety population used for sensitivity analysis.

14.3.2 Analysis of Secondary Endpoints

The analysis of the following secondary endpoint will be carried out using the safety population.

- The rate (%) of clinical success of all the PEEK suture anchors combined at 12 months post-operative will be summarized as described for the analysis of the primary endpoint. This analysis will also be repeated for each of the 2 different types of PEEK suture anchors used in the study.

14.4 SAFETY ANALYSES

- All safety endpoints will be summarized using the safety population. The incidence of events encountered on study will be summarized using frequencies and percentages. An overall AE table will be summarized using the overall incidence according to subjects with at least one AE; subjects with at least one AE by worst severity (mild, moderate, or severe); subjects with at least one AE by worst outcome; subjects with one AE that led to study discontinuation; subjects with at least one AE by relatedness to investigational device; SAEs; ADEs; ASADEs; USADEs and SADEs as applicable. A cumulative summary by the number of events encountered within each classification will also be summarized. The incidence of subjects reporting device deficiencies will additionally be summarized.
- Each of the AE classifications will further be summarized by event using the frequencies (n) and percentages (%) of subjects with each event as well as the cumulative events/episodes per event.
- A listing of concomitant medications will be provided by subject.

CONFIDENTIAL AND PROPRIETARY

This document contains information that is confidential and proprietary to Smith & Nephew PLC and Smith & Nephew, Inc. and is intended for use only by Smith & Nephew and its manufacturer. It shall not be reproduced or copied in whole or in part, nor shall the contents be disclosed by any means without prior written permission from Smith & Nephew, nor shall anyone make any use of it that is contrary to the expressed or implied wishes of Smith & Nephew.

Study Protocol—Device	
PMCF Study on PEEK Suture Anchors for Hip Indications	Number: 2018.14.SMD.PEEK.RET.HIP
	Version: 2.0, 03 April 2019
	Page: 42 of 63

Additional summaries of safety endpoints, if applicable, will be described in the SAP.

14.5 OTHER ENDPOINT ANALYSES

- The analyses of other endpoints will be carried out using the safety population. Overall, device-related failure and device-related re-intervention encountered on-study will be summarized independently as frequencies and percentages. A 95% two-sided exact CI for a single proportion will be presented for each proportion using Clopper-Pearson's method (1934).
- The derivation of surgeon reported outcomes used in summarizing this data for the study will be described in the SAP and will be summarized as appropriate using descriptive summary characteristics for continuous or categorical endpoints at 6 months and 12 months

13.6 Interim Analyses

Not applicable

15. SAMPLE SIZE JUSTIFICATION

This study is precision-based, as a result, the sample size is not based on statistical power calculations.

The sample size for this study is determined based on the feasibility of recruitment, enrollment and follow-up considerations. The study is therefore not powered for any statistical hypothesis testing but will be able to estimate a clinical success rate of 91% with a 95% confidence interval (CI) of 80% to 100%.

CONFIDENTIAL AND PROPRIETARY

This document contains information that is confidential and proprietary to Smith & Nephew PLC and Smith & Nephew, Inc. and is intended for use only by Smith & Nephew and its manufacturer. It shall not be reproduced or copied in whole or in part, nor shall the contents be disclosed by any means without prior written permission from Smith & Nephew, nor shall anyone make any use of it that is contrary to the expressed or implied wishes of Smith & Nephew.

Study Protocol—Device	
PMCF Study on PEEK Suture Anchors for Hip Indications	Number: 2018.14.SMD.PEEK.RET.HIP
	Version: 2.0, 03 April 2019
	Page: 43 of 63

With an assumption of a 91% clinical success rate to be obtained in each of the PEEK anchor sutures and a corresponding 95% CI between 80% and 100%, enrolling between 20 and 120 subjects for each PEEK anchor suture's precision analysis will provide between 15.2% to 95% probability. Thus, an overall minimum of 40 and maximum of 240 subjects who had previously undergone surgery of the hip using PEEK anchor sutures will be enrolled into the study. Additionally, a minimum of 20 subjects will be enrolled at any investigational site.

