4. SYNOPSIS

Title of Study:	PMCF Study on PEEK Suture Anchors for Hip Indications					
Study Design:	Multi-center, retrospective case series.					
Study Type:	Post-market Clinical Follow-up					
Study Products:	
PEEK Suture Anchors for Hip *Part numbers as of September 2018
 
 
 Bioraptor Knotless Suture Anchor	72202397	
 
 SpeedLock Hip Suture Anchor	OM-7500	
 
		Bioraptor Knotless Suture Anchor	72202397	SpeedLock Hip Suture Anchor	OM-7500
Bioraptor Knotless Suture Anchor	72202397					
SpeedLock Hip Suture Anchor	OM-7500					
Intended Use:	The PEEK anchors are intended to be used for soft tissue to bone fixation in the hip following hip capsule repair.					
Study Purpose:	Assess safety and performance post-market of the PEEK suture anchor devices to address clinical data gaps for MDR.					
Primary Outcome:	Evidence of safety and performance of the PEEK suture anchor devices in the hip.					
Statistical Rationale:	The sample size for this study is determined based on the feasibility of recruitment, enrolment and follow-up considerations. The study is therefore not powered for any statistical hypothesis testing but will be able to estimate a clinical success rate of 91% with a 95% confidence interval (CI) of 80% to 100%.					
Sample Size:	
Minimum number of subjects, n=40
 
Maximum number of subjects, n=240
 
Enrollment distribution:
 
Up to three sites will enroll a maximum of 40 subjects per anchor configuration therefore no more than 120 subjects will be enrolled for any anchor type.
					

CONFIDENTIAL AND PROPRIETARY

This document contains information that is confidential and proprietary to Smith & Nephew PLC and Smith & Nephew, Inc. and is intended for use only by Smith & Nephew and its manufacturer. It shall not be reproduced or copied in whole or in part, nor shall the contents be disclosed by any means without prior written permission from Smith & Nephew, nor shall anyone make any use of it that is contrary to the expressed or implied wishes of Smith & Nephew.

Study Protocol—Device	
PMCF Study on PEEK Suture Anchors for Hip Indications	Number: 2018.14.SMD.PEEK.RET.HIP
	Version: 2.0, 03 April 2019
	Page: 21 of 63

	PEEK Anchor	Minimum Number of Subjects/Site	Maximum Number of Subjects/Site	Maximum Number of Subjects for the Study

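### The synopsis and Section 15 promise a 95% CI of 80% to 100% without condition, but at the permitted minimum sizes the planned interval achieves this with probability only 15.2% per anchor (n=20) and 28.9% combined (n=40)

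*Combined protocol and SAP*

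**What the plan says.** The Statistical Rationale row of the synopsis and Section 15 carry the same sentence: the study "will be able to estimate a clinical success rate of 91% with a 95% confidence interval (CI) of 80% to 100" per cent. Both say that feasibility set the size. Section 15 also describes the study as based on precision.

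The next paragraph of Section 15 starts "With an assumption of a 91% clinical success rate to be obtained in each of the PEEK anchor sutures", takes "a corresponding 95% CI between 80% and 100" per cent as the target, and says that 20 to 120 subjects per anchor in the "precision analysis will provide between 15.2% to 95% probability". It concludes: "Thus, an overall minimum of 40 and maximum of 240 subjects". The synopsis repeats the 40 and the 240 but gives no probability.

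Section 14.3.1 defines the primary analysis: "The rate (%) of clinical success of all the PEEK suture anchor devices combined at 6 months post-operative will be summarized", then the same for each anchor. It fixes the interval: "A 95% two-sided exact CI for a single proportion will be presented using Clopper-Pearson's method". No precision is stated anywhere for the combined analysis.

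**The concern.** The sentence presents the 80% to 100% interval as something the study will deliver, whichever permitted size is reached. One paragraph later, Section 15 puts the chance at the lower end of enrolment at 15.2%. The two statements cannot both describe a study that stops at its minimum.

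There is no hypothesis test and no success threshold, so this sentence is what tells a reader how informative the result will be. Someone who reads only the synopsis would expect a lower limit near 80% at any permitted size, and would not learn that this is an unlikely result for a single anchor with 20 subjects. For the combined analysis, which Section 14.3.1 puts first, the reader gets no figure from either place.

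**Working it through.** **Inputs**
- True success rate p = 0.91 for each anchor (Section 15). I assume the same rate for the two anchors combined.
- Target: 95% CI within 80% to 100% (Section 15). An exact interval cannot exceed 100%, so the condition is a lower limit of at least 0.80.
- Interval: two-sided 95% Clopper-Pearson (Section 14.3.1).
- Sizes: 20 to 120 per anchor and 40 to 240 combined (Section 15).

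**Formulas.** For x successes out of n, the lower limit L(x, n) is the 0.025 quantile of the Beta(x, n − x + 1) distribution. Let r be the smallest x with L(x, n) ≥ 0.80. The chance of meeting the target is P(X ≥ r), with X ~ Binomial(n, 0.91).

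**The plan's own figure at n=20.** 19/20 has a lower limit of 0.7513 and fails. 20/20 has 0.025^(1/20) = 0.8316 and passes. So r = 20 and the chance is 0.91^20 = 0.1516. The printed 15.2% reproduces.

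**All four sizes**

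| n | L(r − 1) | r | L(r) | P(X ≥ r) | Mean lower limit | Mean width (points) |
|---|---|---|---|---|---|---|
| 20 (per anchor) | 0.7513 | 20 | 0.8316 | 15.2% | 70.2% | 28.2 |
| 40 (combined) | 0.7961 | 38 | 0.8308 | 28.9% | 77.9% | 19.5 |
| 120 (per anchor) | 0.7925 | 105 | 0.8022 | 92.7% | 84.5% | 10.9 |
| 240 (combined) | 0.7984 | 205 | 0.8031 | 99.8% | 86.7% | 7.6 |

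The chance first reaches 50% at n=48.

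**Results close to the assumed rate.** 18/20 gives 68.3% to 98.8%, and 36/40 gives 76.3% to 97.2%. Both fall short of 80%. 109/120 gives 84.2% to 95.3%.

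**The printed 95% at n=120.** The planned interval gives 92.7%. Other methods come closer to 95%: a Wald interval with both limits inside 80% to 100% gives 15.2% at n=20 and 95.5% at n=120, and a Wald lower limit alone gives 95.9% at n=120. Section 15 names no method, so the source of the 95% cannot be settled from the document.

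**Sensitivity to the assumed rate**

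| True rate | n=20 | n=40 | n=120 |
|---|---|---|---|
| 90% | 12.2% | 22.3% | 85.6% |
| 91% | 15.2% | 28.9% | 92.7% |
| 92% | 18.9% | 36.9% | 97.0% |

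**Sensitivity to discreteness at n=40.** 37/40 has a lower limit of 79.6%. If that counts as meeting a target stated in whole per cents, the chance becomes P(X ≥ 37) = 50.9%.

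**The case against.** The strongest reply is that the plan does not hide the weakness. Section 15 prints the 15.2% straight after the sentence at issue, the figure is correct, and the synopsis says in the same row that feasibility set the size and that the study is not powered. The sentence can be read as what the study could achieve over its permitted range, and near the top of that range it largely holds. That stands for Section 15 read as a whole. It does not rescue the synopsis, which carries no qualifier, or the combined analysis, which has no figure. Nor does the printed range say what it is a probability of.

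A second reply is that 28.9% exaggerates the problem at n=40. The exact probability moves in a sawtooth (n=36 gives 36.0% by the same method), 37/40 misses by 0.4 points, and the mean lower limit of 77.9% is not far from 80%. This is fair, and the figure should carry that caveat. Even so, 50.9% is roughly an even chance and does not support a flat promise. A normal approximation at an observed 91% and n=40, 0.91 ± 1.96 × √(0.91 × 0.09/40), gives 82.1% to 99.9%, but that is not the planned interval.

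Third, the gap between 95% and 92.7% is small and no decision hangs on it. Agreed: it is a side correction.

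**Conclusion.** The concern holds. The sentence claims a precision that the design does not have at its permitted minimum sizes: the chance of achieving it is 15.2% per anchor at n=20 and 28.9% combined at n=40 (50.9% if 79.6% is accepted as 80%). Near the maximum sizes it is mostly met, with 92.7% at n=120 and 99.8% at n=240. The 95% printed for n=120 is 2.3 points above what the planned interval gives (95 − 92.7).

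These figures rest on a true rate of 91% in both anchors, the two-sided 95% Clopper-Pearson interval, and every enrolled subject being analysed. The primary analysis uses the per-protocol population, so the number analysed may be smaller than the number enrolled. No estimate or analysis is affected; what is wrong is the stated precision. It should be fixed.

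**What to change.** In the synopsis and in Section 15, replace the unconditional sentence, and Section 15's probability range, with text such as:

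> The sample size is based on feasibility. If the true clinical success rate is 91%, the probability that the lower limit of the two-sided 95% Clopper-Pearson CI is at least 80% is 15.2% with 20 and 92.7% with 120 evaluable subjects per anchor, and 28.9% with 40 and 99.8% with 240 evaluable subjects combined. At the minimum sizes, 18/20 successes would give a CI of 68.3% to 98.8%, and 36/40 would give 76.3% to 97.2%.

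A short note that 37/40 gives a lower limit of 79.6%, and that counting it would raise 28.9% to 50.9%, would keep the combined figure from being over-read. If the sponsor wishes to keep the 95% at n=120, Section 15 should name the method that produced it.

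The cost is a wording change in two places. Enrolment and analyses stay as they are; the only downside is a less favourable statement of precision.

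### Section 15's 95% precision probability is 92.7% with the specified interval, and both ends of its range count enrolled subjects although the primary analysis is per-protocol

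*Combined protocol and SAP*

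**What the plan says.** Section 15 assumes a 91% success rate for each anchor ("With an assumption of a 91% clinical success rate to be obtained in each of the PEEK anchor sutures") and a 95% interval between 80% and 100%. It then says that "enrolling between 20 and 120 subjects for each PEEK anchor suture's precision analysis will provide between 15.2% to 95% probability". The synopsis, in words repeated in Section 15, says that the study "will be able to estimate a clinical success rate of 91% with a 95% confidence interval (CI) of 80% to 100" percent. No probability is attached to that sentence.

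Section 14.3.1 specifies a two-sided 95% Clopper-Pearson interval for the two anchors combined, and adds: "The same type analysis would be carried out for each of the 2 different PEEK suture anchors used in the study". It also says that the "analyses will be carried out using the per protocol population as the primary analysis population", with the safety population for sensitivity. Section 14.2 limits the per-protocol population to safety-population subjects "who have no significant protocol deviations and who meet all the inclusion/exclusion criteria".

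Section 15 mentions follow-up among the feasibility considerations but gives no number for non-evaluable subjects. Section 11.7 calls loss to follow-up not applicable.

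**The concern.** The probabilities in Section 15 are tied to subjects enrolled, whereas the primary rate is computed on a set that can only be the same size or smaller. The upper figure also does not match the interval that the protocol itself specifies.

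The study is described as precision-based and tests no hypothesis, so this range is the only numerical statement of what the chosen size delivers. If it is too favourable, a reader of the post-market report will expect tighter per-anchor estimates than the design gives. The unqualified sentence in the synopsis adds to this: at the minimum size, the plan's own 15.2% means that the target is missed about 85% of the time.

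**Working it through.** **Inputs.** True rate p = 0.91, target interval 80% to 100%, and n = 20 and 120 per anchor (Section 15). Two-sided 95% Clopper-Pearson interval and per-protocol primary set (Section 14.3.1). Loss rate: not in the documents; 10% and 20% are assumed for illustration. Each subject contributes one outcome.

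**Criterion.** Section 15 does not spell out what the probability refers to. I read it as the chance that the lower limit is at least 0.80; the upper limit cannot exceed 1.

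**Formulas.** For x successes in n, the lower limit is the 0.025 quantile of Beta(x, n − x + 1). When x = n this is 0.025^(1/n). Let x* be the smallest x with lower limit at least 0.80. The probability is P(X ≥ x*), with X binomial(n, 0.91).

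**The plan's figures, all enrolled subjects analysed**
- n = 20: 19/20 has a lower limit of 75.1% and 20/20 has 0.025^(1/20) = 83.2%, so x* = 20. P = 0.91^20 = 0.1516, or 15.2%. Reproduced.
- n = 120: 104/120 has a lower limit of 79.3% and 105/120 has 80.2%, so x* = 105. P = 92.7%, not 95%.

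**Other methods at n = 20 and n = 120**
- Wilson, Jeffreys and Agresti-Coull: 15.2% and 92.7%.
- Wald: 45.2% and 95.9%.
- One-sided 95% Clopper-Pearson bound: 15.2% and 95.9%. This is closest to the stated pair, but it is not the specified interval.
- Half-width of at most 0.10: 15.2% and about 100%.

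**Upper end after loss, from 120 enrolled**

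| Assumed loss | n analysed | x* | Probability |
|---|---|---|---|
| 0% | 120 | 105 | 92.7% |
| 10% | 120 × 0.9 = 108 | 95 | 89.4% |
| 20% | 120 × 0.8 = 96 | 85 | 84.7% |

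The decline is not smooth, because x* moves in whole steps: n = 119 gives 93.2%, 118 gives 89.1% and 114 gives 91.2%.

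**Lower end after loss, from 20 enrolled**
- n = 19: 0.91^19 = 16.7%. n = 18: 18.3%. n = 17: 20.1%. In each case only 100% success qualifies, and a shorter run of successes is more likely.
- n = 16: even 16/16 has a lower limit of 0.025^(1/16) = 79.4%, so the probability is 0.
- The floor follows from 0.025^(1/n) ≥ 0.80, that is n ≥ ln(0.025)/ln(0.80) = 3.689/0.2231 = 16.5, so 17 subjects.
- If each of 20 subjects were lost independently, the chance that 16 or fewer remain would be 13.3% at 10% loss and 58.9% at 20%.

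**Both anchors combined.** n = 40 gives 28.9%, and n = 32 (20% loss) gives 20.4%. At the maximum, n = 240 gives 99.8% and n = 192 gives 99.2%. The target stays attainable.

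**The case against.** The strongest reply is that the documents give no loss rate and loss may be small. Charts are screened against the criteria before enrollment (Sections 11 and 11.6), so few subjects should later fail eligibility. This stands, and it is why the 10% and 20% figures are illustrations only.

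A second reply is that the size was set on feasibility. This also stands: a reader might infer that the precision range is the sole justification for the sample size, but Section 15 and the synopsis both say otherwise. No decision rule depends on the range. It is still a stated property of the design and should be correct.

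A third reply is that the sponsor may have used a different criterion. With the one-sided bound, 10% and 20% loss would give about 94% and about 91%, and the target would become unreachable only at 13 or fewer. Section 15 names no such criterion, and Section 14.3.1 specifies the two-sided interval.

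Two stronger readings are tempting. One is that a subject seen only at, say, month 14 must drop out of the 6-month analysis, since one visit within the inclusion window is enough to qualify. Neither Section 14.2 nor Section 14.3.1 requires an in-window visit, and a later chart might still show 6-month status. The documents leave this open, and Section 14 defers detail to a SAP to be finalised before database lock. The other is that any modest loss harms the minimum size. Losing 1 to 3 of 20 does not; it takes at least 4 of 20.

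**Conclusion.** The point holds in limited form. The 15.2% is exact for 20 analysed subjects. The 95% is 2.3 points too high for the specified interval, and that gap has nothing to do with loss. Per-protocol exclusions would lower the upper figure further, to 89.4% at 10% or 84.7% at 20%, if losses of that size occurred.

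At the minimum, the 80% lower limit becomes unreachable for an anchor with 16 or fewer evaluable subjects. A reader might infer that the study as a whole could not meet its target; the combined analysis does not support that.

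The result rests on p = 0.91, on reading the criterion as a lower limit of at least 80%, on one outcome per subject, and on assumed loss rates. The statement that the study can deliver the 80% to 100% interval needs qualifying whatever the loss rate, because at 20 per anchor the plan's own figure is 15.2%.

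**What to change.** In Section 15:
- Replace 95% with 92.7%, or state the different criterion that gives 95%.
- Say that the probability is the chance that the two-sided Clopper-Pearson interval lies within 80% to 100%.
- Give it for evaluable per-protocol subjects per anchor over an assumed loss range, for example 0%, 10% and 20%, labelled as an assumption.
- Note that with fewer than 17 evaluable subjects for an anchor, the 80% lower limit cannot be reached even with no failures.

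In Section 15 and the synopsis, qualify the sentence on achievable precision with the probability at the minimum size (15.2% per anchor if all 20 are evaluable).

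The cost is a few restated figures and a less favourable upper number. Enrollment, endpoints and analysis methods do not change.
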